6.12 Correlative Research

A mandatory correlative research component is part of this study, the patient will be automatically registered onto this component (see Sections 3.19c, 3.19d, 14.1 and 17.1).

6.13 Documentation of IRB approval must be on file with ACCRU before an investigator may register any patients. Approvals should be uploaded through the online ACCRU Regulatory Management System (ARMS).

In addition to submitting initial IRB approval documents, ongoing IRB approval

documentation must be on file with ACCRU no less than annually. Approvals should be uploaded through the online ACCRU Regulatory Management System (ARMS). If the necessary documentation is not submitted in advance of attempting patient registration, the registration will not be accepted and the patient may not be enrolled in the protocol until the situation is resolved.

Submission of annual IRB approvals to ACCRU is required until the study is closed through your IRB.

6.14 Prior to accepting the registration/randomization, the registration/randomization application will verify the following:

- IRB approval at the registering institution
- Patient eligibility
- Existence of a signed consent form
- Existence of a signed authorization for use and disclosure of protected health information

6.15 At the time of registration, the following will be recorded:

- Patient has/not given permission to store and use his/her sample(s) for future research to learn about, prevent, or treat cancer.
- Patient has/not given permission to store and use his/her sample(s) for future research to learn, prevent, or treat other health problems (for example: diabetes, Alzheimer's disease, or heart disease).
- Patient has/not given permission for ACCRU to give his/her sample(s) to outside researchers.

6.16 Treatment cannot begin prior to registration and must begin  $\leq 7$  days after registration.

6.17 Pretreatment tests/procedures (see Section 4.0) must be completed within the guidelines specified on the test schedule.

6.18 All required baseline symptoms (see Section 10.5) must be documented and graded.

6.19 Treatment on this protocol must commence at an ACCRU/ITOG institution under the supervision of a medical oncologist or endocrinologist for the administration and management of placebo/selumetinib therapy. Collaboration with a nuclear medicine physician will also be necessary to coordinate the conduct and administration of  $^{131}\text{I}$  therapy.

6.2 Randomization Procedures

6.21 The factors defined in Section 5.0, together with the registering membership, will be used as stratification factors.

6.22 After the patient has been registered into the study, the values of the stratification factors will be recorded, and the patient will be assigned to one of the following treatment groups using the Pocock and Simon dynamic allocation procedure which balances the marginal distributions of the stratification factors between the treatment

groups (Pocock-Simon ref – see below).

- Radioactive iodine (RAI) plus placebo
- Radioactive iodine plus selumetinib

### 6.3 Procedures for Double-Blinding the Treatment Assignment

6.31 AstraZeneca will supply selumetinib or placebo to Clinical Research Services, a division of Rx Crossroads by McKesson for distribution to participating sites. No blinded starter supplies will be available for this study. Blinded, patient-specific clinical supplies will be sent to the registering investigator at the time of randomization and should arrive within 3-5 days. This randomization will be performed by the ACCRU Statistical and Data Center. The assigned ACCRU Patient ID number must be recorded by the registering institution for proper bottle dispersion. Once a patient has been registered, ACCRU will electronically transmit a clinical drug request for that patient to Clinical Research Services, a division of Rx Crossroads by McKesson. This request will be entered and transmitted by ACCRU the day the patient is registered and will be processed and shipped by Clinical Research Services, a division of Rx Crossroads by McKesson the same business day if received before 2 pm ET. If the request is received after 2 pm ET, drug will be shipped the following business day. Shipments will be sent via FedEx Priority Overnight.

6.32 Each blinded, patient-specific supply will be labeled with:

- The study protocol number (i.e., ACCRU RU241306I)
- The patient study ID number
- The patient's initials
- The number of capsules
- Administration instructions (i.e., 'Administer as directed per Protocol ACCRU RU241306I')
- Drug Identification (i.e., Selumetinib 25 mg OR Placebo)
- Expiration Date
- Storage instructions ("Store at controlled room temperature, 25°C (77°F)")
- Date dispensed
- IND caution statement and/or local regulatory statements
- Emergency contact instructions

6.33 Please see section 15.18 for more information on how to re-order more supplies, if needed.

## 7.0 Protocol Treatment

(Please refer to the table in Section 4.0 for schedule of all protocol treatments and assessments)

### 7.1 Treatment Schedule

Agent	Dose Level	Route	Day	ReRx
Selumetinib or Placebo*	75 mg	PO	BID	None
Thyrogen™	0.9 mg	IM	Daily for 2 days prior to RAI for therapy	
RAI (  I)	100-150 mCi**	PO	Once	None

\* The twice daily doses of selumetinib should be scheduled 12 hours apart (+/- 2 hours). If a participant misses a scheduled dose by more than 2 hours, that dose should not be given and the next dose administered at the regularly scheduled time. It is not required to extend the time on Selumetinib or placebo to make up missed doses unless extending time (i.e. extending time on treatment and/or instituting treatment interruptions) is deemed necessary to comply with instructions detailed below. The period of time on placebo or selumetinib (i.e. the time on treatment including treatment interruptions) is not to exceed 8 weeks.

\*\* Patients < 70 years of age will be treated with 150 mCi I (+/- 5 mCi). Patients ≥ 70 years of age can be treated with a I activity from 100 mCi up to and including 150 mCi (+/- 5 mCi for 100 mCi or 150 mCi administered activities); for these patients, the activity to be administered must be determined by the investigator at the time of study registration. Though performing whole blood and body dosimetry to determine maximum tolerated activity (MTA) is NOT required, for centers at which this evaluation *is* done prior to therapeutic I study administration (Week 4), lower therapeutic I activities than what is recommended here may be administered if the MTA is calculated to be lower than the lower limit of what is allowed per protocol or what has been determined to be given (for patients ≥ 70 years of age). *Examples* (these are applicable only in instances in which dosimetry was performed prior to therapeutic I administration): 1) *Patients <70 years of age*: If the dosimetry-determined MTA value is less than 150 mCi, then an RAI activity less than 150 mCi may be administered; 2) *Patients ≥70 years of age*: If the dosimetry-determined MTA value is less than the activity that was determined to be given at the time of study registration, then a lower RAI activity may be administered, even activities less than 100 mCi if the MTA is below this threshold. Dosimetry can NOT be used to justify administering therapeutic I activities higher than what has been recommended per this protocol.

Administration of Thyrogen™ and/or therapeutic I at a facility other than the participating site is allowed if documentation of the dates and amount/activity of drug /radioisotope administered is provided to verify adherence to protocol requirements. Performance of post-therapy iodine scans is not required, but is allowed per institutional practice.

#### **Placebo or Selumetinib**

Continuous dosing of placebo or selumetinib 75 mg orally twice daily will be started on Week 1, Day 1 and continued through 2 days after therapeutic I therapy has been administered.

Below are recommendations to be followed for therapy with both selumetinib and placebo:

Selumetinib/placebo should be taken twice a day on an empty stomach (1 hour before or 2 hours after a meal), 12 hours ( $\pm$  2 hours) apart with a glass of water.

- Patients should avoid excessive sun exposure and use adequate sunscreen protection if sun exposure is anticipated.
- Patients should not donate blood during the study.
- Unless clinically indicated, patients should avoid changes to, or the addition of, concomitant medications, in particular any that may affect the metabolism of selumetinib (e.g., CYP1A2, CYP2C19 or 3A4 inhibitors/inducers).

The pharmacokinetics of Selumetinib were investigated in study D1532C00086, conducted in the UK involving healthy volunteers of Asian ethnicity (defined as being born in an Asian country, and expatriate for not longer than 5 years, and with maternal and paternal grandparents of Asian ethnicity). The subjects who received Selumetinib in Study D1532C00086 were of the following ethnicities: Japanese, Chinese, Filipino, Malay, Malaysian, Maldivian, Singaporean, Thai, Indian and Vietnamese, and it is not known in these groups whether Selumetinib exposure will be similar to Western subjects or to subjects of the specific Asian ethnicities included in Study D1532C00086.

The pharmacokinetic findings from study D1532C00086 do not support excluding subjects of Asian ethnicity from studies of Selumetinib. However, as it is possible that Asian subjects may experience higher Selumetinib plasma exposure (than would be expected in Western subjects receiving the same dose of selumetinib), there could be a potential for a higher risk of adverse events.

The number of Asian patients with advanced cancer who have received treatment with Selumetinib is very low. Emerging information from ongoing study D1532C00067 of Japanese patients receiving selumetinib + docetaxel for second-line treatment of NSCLC suggests that febrile neutropenia may occur more commonly in Japanese patients (3 of 8 patients treated, although comparative data in Japanese patients receiving docetaxel monotherapy is not available) than might be predicted from studies conducted in Western subjects.

Patients of Asian ethnicity are not excluded from studies evaluating Selumetinib. However, when considering enrolling an individual of Asian ethnicity to a Selumetinib clinical study, investigators should make a clinical judgment as to whether the potential risk of experiencing higher Selumetinib plasma levels outweighs the potential benefit of treatment with Selumetinib. The Patient Information and Consent form for studies of Selumetinib includes information on the possibility of higher Selumetinib plasma levels and occurrence of adverse events in Asian subjects than in subjects who are not of Asian origin. Investigators should be aware of the potentially higher risk of adverse events when monitoring patients of Asian ethnicity receiving treatment in clinical studies of Selumetinib.

As reproductive toxicology data indicate that selumetinib has adverse effects on embryofoetal development and survival at dose levels that do not induce maternal toxicity in mice, the following restrictions apply:

Selumetinib/placebo should not be administered to pregnant or breast-feeding women and conception while on treatment must be avoided. Female patients of child-bearing potential will be required to use reliable methods of contraception for the duration of the study and until

4 weeks after the last dose of Selumetinib. Of note, patients may be requested to maintain contraception and avoid pregnancy for a longer period of time after  $^{131}\text{I}$  administration according to institutional guidelines.

Male patients with sexual partners who are pregnant or who could become pregnant (i.e., women of child-bearing potential) should use acceptable methods of contraception for 3 months after the last dose of selumetinib/placebo to avoid pregnancy and/or potential adverse effects on the developing embryo. Of note, patients may be requested to maintain contraception and avoid pregnancy for a longer period of time after  $^{131}\text{I}$  administration according to institutional guidelines.

Selumetinib/placebo capsules contain vitamin E in the form of D- $\alpha$ - Tocopheryl polyethylene glycol 1000 succinate (TPGS), a water-soluble form of vitamin E which acts as a formulation excipient. The maximum daily dose of vitamin E that a study subject may receive from selumetinib/placebo is approximately 261.6 mg/day. Therefore:

Patients should not take any supplemental vitamin E. High doses of vitamin E have been reported to cause bleeding and interrupt blood coagulation processes.

Selumetinib/placebo should be administered with caution in patients who are also receiving concomitant Coumadin anticoagulant medications, e.g. warfarin. These patients should have their INR monitored/anticoagulation assessments conducted more frequently and the dose of the anticoagulant should be adjusted accordingly.

### **$^{131}\text{I}$ Therapy**

Patients  $<70$  years of age will be treated with 150 mCi  $^{131}\text{I}$  ( $+/-.5$  mCi). Patients  $\geq 70$  years of age can be treated with  $^{131}\text{I}$  activity from 100 mCi up to and including 150 mCi ( $+/-.5$  mCi for 100 mCi or 150 mCi administered activities); for these patients, the activity to be administered must be determined by the investigator at the time of study registration.

These  $^{131}\text{I}$  activities are within the 100-200 mCi range for empiric RAI treatment of metastatic thyroid cancer recommended by the 2015 American Thyroid Association (ATA) guidelines (Haugen et al, 2015) Allowing activities  $<150$  mCi for patients  $\geq 70$  years of age as detailed above acknowledges that the  $^{131}\text{I}$  maximum tolerable activity (MTA) tends to decline among the elderly population (Tuttle et. al., 2006); (Kulkarni et. al, 2006).

Though performing whole blood and body dosimetry to determine maximum tolerated activity (MTA) is NOT required, for centers at which this evaluation is done (performed during the study or within 6 months of study enrollment), lower therapeutic  $^{131}\text{I}$  activities than what is recommended here may be administered if the MTA is calculated to be lower than the lower limit of what is allowed per protocol (i.e. for patients with MTA values  $< 150$  mCi for patients  $<70$  years of age or  $<100$  mCi for patients  $\geq 70$  years of age). Dosimetry can NOT be used to justify administering therapeutic  $^{131}\text{I}$  activities higher than what has been recommended per this protocol. Performance of post-therapy iodine scans is not required, but certainly allowed per institutional practice.

Administration of Thyrogen™ and/or therapeutic  $^{131}\text{I}$  at a facility other than the participating site is allowed if documentation of the dates and amount/activity of drug /radioisotope administered is provided to verify adherence to protocol requirements.

Any form of oral  $^{131}\text{I}$  (e.g., capsule or liquid) is allowed on the trial.

7.2 Patients can be instructed in selumetinib administration techniques and granted treatment independence with nursing staff approval.

7.3 For this protocol, the patient must return to the consenting ACCRU institution for evaluation during treatment and during observation (Active Monitoring Phase) according to the table in Section 4.0.

7.4 Treatment by a local medical doctor: Administration of Thyrogen™ and/or therapeutic I at a facility other than the participating site is allowed if documentation of the dates and amount/activity of drug /radioisotope administered is provided to verify adherence to protocol requirements.

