administered must be determined by the investigator at the time of study registration. Though performing whole blood and body dosimetry to determine maximum tolerated activity (MTA) is NOT required, for centers at which this evaluation is done prior to therapeutic  $^{131}\text{I}$  study administration (Week 4), lower  $^{131}\text{I}$  activities than what is recommended here may be administered if the MTA is calculated to be lower than the lower limit of what is allowed per protocol or what has been determined to be given (for patients  $>70$  years of age). **Examples** (these are only applicable in instances in which dosimetry was performed prior to therapeutic  $^{131}\text{I}$  administration): *1) Patients  $<70$  years of age:* If the dosimetry-determined MTA value is less than 150 mCi, then a RAI activity less than 150 mCi may be administered; *2) Patients  $>70$  years of age:* If the dosimetry-determined MTA value is less than the activity that was determined to be given at the time of study registration, then a lower RAI activity may be administered, even activities less than 100 mCi if the MTA is below this threshold. Dosimetry can NOT be used to justify administering therapeutic  $^{131}\text{I}$  activities higher than what has been recommended per this protocol. Administration of ThyrogenTM and/or therapeutic  $^{131}\text{I}$  at a facility other than the participating site is allowed if documentation of the dates and amount/activity of drug /radioisotope administered is provided to verify adherence to protocol requirements. Performance of post-therapy iodine scans is not required, but is allowed per institutional practice.

6. CT(s) WITHOUT CONTRAST (refer to footnote 14) and/or MRI(s) for tumor(s) assessment is/are to be done prior to study registration, about 3 months ( $\pm$  1 week) after  $^{131}\text{I}$  therapy, and then every 3 months ( $\pm$  1 week). After 12 months post- $^{131}\text{I}$  therapy, follow up scans are to be done every 6 months ( $\pm$  1 week) for a maximum of 2 years ( $\pm$  3 months) from study randomization. The schedule of radiographic assessments may be altered in order to maintain the tumor assessment intervals detailed here in the event unscheduled assessments are performed. Every effort must be made to have the 6 month post- $^{131}\text{I}$  therapy assessment(s) performed.

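### For patients aged 70 or over, the protocol states two different conditions under which dosimetry permits a 131I activity lower than the one fixed at registration

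*Combined protocol and SAP*

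**What the plan says.** All four places that describe therapeutic 131I give patients aged 70 or over an activity from "100 mCi up to and including 150 mCi", and require it to be set in advance: "for these patients, the activity to be administered must be determined by the investigator at the time of study registration". Dosimetry to find the MTA is optional in all of them. They part on what an MTA result allows.

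- **Section 7.1, text headed 131I Therapy.** A lower activity may be given "if the MTA is calculated to be lower than the lower limit of what is allowed per protocol (i.e. for patients with MTA values" below 150 mCi for patients under 70, or below 100 mCi for patients aged 70 or over. No other condition is given. The dosimetry that counts is that "performed during the study or within 6 months of study enrollment".
- **Section 7.1, table footnote.** The MTA may be "lower than the lower limit of what is allowed per protocol or what has been determined to be given (for patients" aged 70 or over). The footnote then gives an example for this age group: "If the dosimetry-determined MTA value is less than the activity that was determined to be given at the time of study registration", a lower activity may be given, even below 100 mCi if the MTA is below that.
- **Section 4.0, footnote 5.** It has the same two-part condition and the same example, but both are written for patients over 70. The timing wording is "for centers at which this evaluation is done prior to therapeutic" administration at Week 4, with no look-back limit.
- **Section 15.31.** It has the same two-part condition. The rule is written for patients aged 70 or over and its example for patients over 70.

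**The concern.** Two rules for the same decision stand in current text, two of the four statements being within Section 7.1 itself. The 131I Therapy text offers, as grounds to lower the activity of an older patient, only an MTA below 100 mCi. The other three also offer an MTA below the activity already registered. A site that works from the 131I Therapy text finds no clause letting it depart from the registered activity when the measured MTA is below that activity but not below 100 mCi.

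Two things are at stake. One is patient handling: the same result can be handled differently depending on the section a site reads, in the age group whose MTA, by the protocol's own account, tends to decline. The other is the meaning of adherence. 131I is given in both arms, the primary endpoint is response six months after it, and it may be given at outside facilities on condition that records allow adherence to be checked. A reduced activity could be checked as adherent against one section and as a deviation against another.

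**Working it through.** The plan has no figure to reproduce here; the check is a comparison of texts. Set side by side for older patients:

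| Place | MTA result that permits a lower activity | Age wording | Dosimetry that counts |
|---|---|---|---|
| 7.1, 131I Therapy | below 100 mCi | 70 or over | during the study or within 6 months of enrolment |
| 7.1, table footnote | below 100 mCi, or below the registered activity | 70 or over | before Week 4 administration |
| 4.0, footnote 5 | as the table footnote | over 70 (rule and example) | before Week 4 administration |
| 15.31 | as the table footnote | 70 or over (rule); over 70 (example) | before Week 4 administration |

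**Where the conditions disagree.** Let A be the activity fixed at registration (100 to 150 mCi) and M the measured MTA.

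- 131I Therapy text: permission if M < 100.
- Other three texts: permission if M < 100 or M < A.

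Both give permission when M < 100, and neither does when M is at least A. They differ exactly when 100 ≤ M < A. In whole mCi:

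- A = 100: no disagreement.
- A = 110: M from 100 to 109.
- A = 125: M from 100 to 124.
- A = 150: M from 100 to 149.

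In every such case the registered activity exceeds the MTA. The largest difference is 150 − 100 = 50 mCi, before the ±5 mCi tolerance.

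**Example.** Registered activity 150 mCi, MTA 120 mCi. Since 120 < 150, three texts expressly permit a lower activity. Since 120 is not below 100, the 131I Therapy text gives no such permission.

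**Patients under 70.** All four texts give the same threshold, an MTA below 150 mCi, so there is no conflict.

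**Age boundary.** A patient aged exactly 70 falls outside the registered-activity condition as Section 4.0 footnote 5 words it, but inside it in the Section 7.1 table footnote. Section 15.31 differs between its rule and its example.

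**Dosimetry timing.** A result obtained nine months before enrolment is outside the look-back in the 131I Therapy text. The other three state no such limit.

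**The case against.** The strongest reply is that the 131I Therapy text is silent rather than contrary. What it recommends for patients aged 70 or over is a range, so its clause on lower activities can be read as dealing only with going below the 100 mCi floor. On that reading an activity of 120 mCi is already allowed, and the table footnote in the same section settles the rest with an example. This has some force, but it does not remove the problem. The same text requires the activity to be fixed at registration and then says nothing on changing it within the range, while its explanatory parenthesis spells out the condition as an MTA below 100 mCi for this group.

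Other parts of the reply stand and limit the point:

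- A reader might infer that the 131I Therapy text obliges or specially allows a site to exceed the MTA, by 150 − 120 = 30 mCi in the example. The documents do not support this. Every version says a lower activity *may* be given; none requires a reduction, and none forbids an activity above the MTA. The difference is a missing permission.
- A reader might infer that every older patient with an MTA in the disputed band is affected. Dosimetry is optional, and an MTA known before registration can inform the activity that is fixed. The gap matters mainly when the result comes later, which the protocol foresees because dosimetry may be done during the study.
- A reader might take the dosimetry windows as a second contradiction. They are compatible, since dosimetry that guides the activity has to precede it. One text adds a look-back limit that the others leave unstated.
- A reader might infer bias between arms. Activity already varies by design in this age group, treatment is double-blind, and both age 70 or over and registering membership are balancing factors. The documents show no mechanism that would favour an arm.

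**Conclusion.** The contradiction is real and in current text. For patients aged 70 or over, the four statements disagree on whether dosimetry permits a lower activity whenever the MTA is at least 100 mCi and below the registered activity. This band is empty at 100 mCi registered and runs from 100 to 149 mCi at 150 mCi registered. The age boundary is inconsistent as well, and the dosimetry look-back appears in one place only.

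The consequence is uneven handling of patients and uncertainty over what counts as a deviation. It is not an instruction to exceed the MTA, and it is not a threat to the comparison of arms. The conclusion rests on reading the parenthesis in the 131I Therapy text as defining the condition, and on the registered activity being binding once set. The documents do not say how many patients will be aged 70 or over or how many centres will do dosimetry, so the number affected cannot be estimated. The point should be corrected, but it does not call the design into question.

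**What to change.** Reconcile Section 4.0 footnote 5, the Section 7.1 table footnote, the Section 7.1 text headed 131I Therapy, and Section 15.31 into a single statement. It should settle three things:

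1. which MTA results permit an activity lower than the one fixed at registration;
2. whether patients aged exactly 70 belong to the older group for this purpose;
3. which dosimetry qualifies, including whether a look-back limit applies.

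Use that statement word for word in Sections 4.0, 7.1 and 15.31. Which rule is adopted is for the clinical team to decide; nothing here favours one. The cost is a wording change to the protocol, with no added procedure and no effect on sample size or analysis.
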